7. STATISTICAL CONSIDERATIONS

Full details on the statistical analyses to be performed will be provided in a separate statistical analysis plan (SAP).

7.1. Sample Size Determination

As outlined in [Section 3](#), the sample size for **Cohorts E** will be determined by the assessment of safety observed during the DLT period. It is expected that between 3 and 6 patients will be enrolled within each dosing cohort for a total sample size ranging from 6 to 12.

7.2. Analysis Population

The full analysis set (FAS) population includes all eligible patients who receive at least 1 dose of study drug. Analyses for the FAS population will be conducted based on the actual treatment received. Unless otherwise specified, the FAS population is the primary population for all efficacy and safety analyses.

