After 2 hours the patient should void the instilled suspension directly into a toilet. After bladder evacuation, the next first voided urine sample should be collected for PVSRIPO Shedding.

The patient should be advised to limit their fluid intake for 4 hours prior to instillation and until bladder evacuation is permitted (i.e. 2 hours after instillation).

For **Cohort F**: Each patient will receive the following sequence of bladder washes prior to instillation of PVSRIPO: 100 ml saline followed by 75 ml 5% DDM followed by 100 ml saline. A urinary catheter will be inserted into the urethra under aseptic conditions according to local hospital protocol and the bladder drained completely. Using a catheter adapter with the syringe, each successive wash will be instilled over a period of several minutes per local practice. Each saline wash will be retained in the bladder for approximately 5 minutes and the 5% DDM wash will be retained within the bladder for 15 (± 5) minutes. At the end of each retention period, the bladder will be drained completely, and the next wash applied. Upon completion of the three washes, PVSRIPO will be instilled as described for Cohort E and in the Pharmacy manual. The process for pretreatment washes has been adapted from the process described for CG0070.

The dose administered to each patient enrolled in **Cohort F** will be the highest dose evaluated in Cohort E that does not exceed the maximum tolerated dose.

Reference therapy, dosage, and mode of administration: Not applicable.

Criteria for evaluation:**Efficacy:**

Since NMIBC is not routinely detected on imaging, it is not possible to assess responses to anti-cancer therapy using traditional oncology imaging endpoints like overall response rate (ORR). Therefore, histologic evaluation of surgical specimens after treatment is the most sensitive way to assess tumor response to PVSRIPO administration with a focus on quantifying the proportion of patients who have demonstrable infection of tumor tissue.

Safety: Safety will assess the frequency of DLTs observed during the 14 days following administration of PVSRIPO, evaluated by monitoring AEs, clinical laboratory test results

(hematology, clinical chemistry, and coagulation), vital sign measurements (blood pressure, heart rate [HR], and oral body temperature), and physical examination findings.

Statistical methods:

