2. OBJECTIVES AND ENDPOINTS

Objectives and endpoints described in **Table 3** are *in addition* to those described in the master protocol (see [Master Protocol Section 2 \[Objectives and Endpoints\]](#)) and include those specific for **Cohort E and F**. Note that two cohorts of patients will be enrolled: **Cohort E** will include patients with recurrent NMIBC intended for TURBT or cystectomy who will receive PVSRIPO via intravesical instillation and **Cohort F** will include patients with recurrent NMIBC intended for TURBT or cystectomy who will receive PVSRIPO via intravesical instillation after a sequence of 5% DDM and saline washes.

Note that the NMIBC sub study will NOT be treating patients with the combination of PVSRIPO and anti-PD-1/L1, i.e., Phase 2 will not be enrolled in the NMIBC substudy.

Table 3: Objectives and Endpoints *

Objectives	Endpoints
Primary Objectives and Endpoints Phase 1	
Cohort E: To evaluate the safety and tolerability of PVSRIPO monotherapy administered by intravesical instillation to patients with recurrent NMIBC intended for TURBT or cystectomy.	Proportion of patients who undergo TURBT or cystectomy as scheduled. This endpoint replaces the master protocol endpoint described as “proportion of patients who received 1, 2 and 3 injections of PVSRIPO”.
Cohort F: To evaluate the safety and tolerability of PVSRIPO monotherapy administered by intravesical instillation after a sequence of 5% DDM and saline washes to patients with recurrent NMIBC intended for TURBT or cystectomy.	Proportion of patients who undergo TURBT or cystectomy as scheduled. This endpoint replaces the master protocol endpoint described as “proportion of patients who received 1, 2 and 3 injections of PVSRIPO”.
Secondary Objectives and Endpoints Phase 1	
Cohorts E and F: To assess the ability of PVSRIPO administered as monotherapy via intravesical instillation (Cohort E) or intravesical instillation after a sequence of 5% DDM and saline washes (Cohort F) to infect bladder cancer cells in patients with recurrent NMIBC intended for TURBT or cystectomy	Proportion of patients with evidence of PVSRIPO infection in resected tissues. This endpoint replaces the master protocol antitumor efficacy endpoints which include ORR, CBR, DOR, PFS and OS.

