3. INVESTIGATIONAL PLAN

The overall study design, including the dose limiting toxicity (DLT) definitions can be found in the master protocol ([Master Protocol Section 3.1 \[Overall Study Design\]](#)). This section focuses on those aspects of the study design specific to patients with recurrent NMIBC.

[figure not shown]
Since the purpose of this substudy is to evaluate different methods of administration of PVSRIPO into tumors located within the bladder mucosa, the NMIBC substudy will **NOT be treating patients with the combination of PVSRIPO and anti-PD-1/L1, i.e., Phase 2 will not be enrolled.**

Two cohorts of patients will be enrolled in this portion of the study. Both **Cohort E and F** will evaluate the administration of PVSRIPO monotherapy in patients with recurrent NMIBC intended for TURBT or cystectomy; patients enrolled in **Cohort E** will receive PVSRIPO via intravesical instillation while patients enrolled in **Cohort F** will receive PVSRIPO via intravesical instillation after a sequence of 5% DDM and saline washes.

Cohort E: Because the dose for PVSRIPO administered by intravesical instillation has not been determined, **Cohort E** has been designed to evaluate 2 different dose levels of PVSRIPO using a 3+3 dose escalation approach ([Figure 1](#)). Three patients will initially be treated with a total dose of 2×10^9 TCID₅₀ (**Low Dose Cohort E**) administered by intravesical instillation and the frequency of DLTs assessed. The decision to escalate/de-escalate the PVSRIPO dose will be based on the presence of DLTs observed during the 14 days following administration of PVSRIPO in consultation with the independent Data Safety Monitoring Committee (DSMC).

Provided that none of the initial 3 patients experience a DLT, the dose will be considered not to have exceeded the maximally tolerated dose (MTD) and the next cohort of patients (n=3) will receive a total dose of 1×10^{10} TCID₅₀ (**High Dose Cohort E**) via intravesical instillation.

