6.4. Data Safety Monitoring Committee

The external independent DSMC is described in the Master Protocol. The text below is specific for patients enrolled in **Cohort E and F**. The schedule of meetings is as follows:

- When dose escalation/de-escalation decisions are required ([Section 3](#)) prior to initiating enrollment in the next cohort. For example, prior to opening the 1×10^{10} TCID₅₀ intravesical instillation dose in **Cohort E** or prior to opening **Cohort F**.
- Additional reviews may occur based on DSMC requests.
- The DSMC will review any Suspected Unexpected Serious Adverse Reaction (SUSAR) that occurs during the study and may recommend enrollment be paused until the event is reviewed.

Note that the timing of DSMC meetings as outlined in [Section 6.3 of the Master Protocol](#) are superseded by the text above. This change is implemented because the structure of the Phase 1 portion of this substudy is slightly different than that described in the Master Protocol, i.e. the timings outlined in the [Section 6.3 of the Master Protocol](#) are not applicable.

Note that the text below from [Section 6.3 of the Master Protocol](#) will still apply to this substudy.

During the study, accrual of patients will be suspended for the following safety events pending evaluation and recommendations by the DSMC:

- Any Grade 5 AE considered to be at least possibly related to study drug(s).
- If two or more of up to 6 DLT-evaluable subjects in **Cohort E** experience DLTs.
- A death within 30 days of study treatment (other than death related to progressive disease).
- Any unexpected Grade 4 AE considered at least possibly related to study drug(s).

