7.4.5. Safety Analyses

Refer to [Section 7.4.5 of the Master Protocol](#).

Additional safety analyses specific for NMIBC will include the number and percentage of patients who undergo TURBT or cystectomy.

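### Section 7.2 makes eligibility a condition of the only analysis set used for safety, so a dosed but ineligible patient can be left out of the adverse event summaries and the primary surgery endpoint

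*Combined protocol and SAP*

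**What the plan says.** Section 7.2 contains one analysis set, and the synopsis repeats it: "The full analysis set (FAS) population includes all eligible patients who receive at least 1 dose of study drug". Patients are analysed by the treatment they actually received. The set's role is then fixed: "Unless otherwise specified, the FAS population is the primary population for all efficacy and safety analyses". No all-treated safety set appears anywhere in the substudy protocol.

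Two kinds of result fall under safety here.

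- **Surgery.** The primary endpoint for both cohorts (Section 2, Table 3) is "Proportion of patients who undergo TURBT or cystectomy as scheduled". Section 7.4.5 places it among the safety analyses: "Additional safety analyses specific for NMIBC will include the number and percentage of patients who undergo TURBT or cystectomy".
- **DLTs.** The synopsis, under criteria for evaluation, states: "Safety will assess the frequency of DLTs observed during the 14 days following administration of PVSRIPO".

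The remaining safety methods are deferred to Section 7.4.5 of the master protocol, and full analysis detail to a separate SAP. Neither is in the file.

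On timing, Section 6.1 places the eligibility decision after consent and before treatment. Nothing says what happens to a patient whose breach comes to light after dosing.

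**The concern.** The primary objective is safety and tolerability, and for that purpose the natural denominator is everyone exposed. Section 7.2 adds a second condition, eligibility, which has nothing to do with exposure.

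Several criteria in Sections 4.1 and 4.2 rest on history that can be incomplete on the day of dosing: intravesical agents in the previous 3 months, vesicoureteric reflux, variant histology, prior T2 disease. Section 6.3 allows archival tissue to be collected up to 2 months after enrollment, which is later than both the 14-day DLT window and the Day 30 visit. A breach could therefore be recognised when the patient's adverse events and surgical outcome are already known, in a study with no comparator and no blinding described.

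A patient who did badly is also the one whose history is most likely to be looked at again. Removing that patient would make the reported safety results look better than what happened. With three to six patients per dose group, a single removal is visible in every percentage.

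**Working it through.** **1. Which results use the restricted set**

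| Item | Where | Population named | Does the eligibility condition apply? |
|---|---|---|---|
| Surgery as scheduled (primary) | Section 2; Section 7.4.5 | None, so the Section 7.2 default | Yes, as written |
| Adverse event summaries | Section 7.4.5, deferring to the master protocol | None here, so the Section 7.2 default | Yes, unless the master protocol says otherwise |
| Reported DLT frequency | Synopsis | None here; DLT definitions are in the master protocol | Cannot be settled from these documents |
| Escalation and de-escalation | Section 3 | Patients treated and observed for 14 days | No |
| Suspension of accrual | Section 6.4 | DLT-evaluable subjects, not defined here | Not shown |

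The two real-time rules have their own basis. Section 3 says: "The decision to escalate/de-escalate the PVSRIPO dose will be based on the presence of DLTs observed during the 14 days following administration of PVSRIPO". Section 6.4 counts "If two or more of up to 6 DLT-evaluable subjects in" Cohort E. Neither refers to the FAS.

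**2. Sample size**

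Section 7.1 gives 6 to 12 patients for Cohort E. Two dose levels of 3 to 6 patients give 2 × 3 = 6 and 2 × 6 = 12, so the range reproduces. Adding 3 for Cohort F gives 9 to 15. (The synopsis also states 3 to 12 for Cohort E, which would make the total 6 to 15.) One patient is then 1/15 = 6.7% to 1/9 = 11.1% of the substudy, 1/6 = 17% of an expanded dose group and 1/3 = 33% of a group of three.

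**3. Effect of one exclusion, if the excluded patient is the one with the event**

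With x events in n patients, dropping a patient with a DLT gives (x − 1)/(n − 1). Dropping a patient who missed surgery leaves x successes in n − 1. The intervals are exact 95% (Clopper-Pearson) and are added for illustration; Section 7.4.1 plans descriptive summaries only.

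| Result | All dosed | Eligible only |
|---|---|---|
| Surgery as scheduled, group of 6 | 5/6 = 83% (36% to 99.6%) | 5/5 = 100% (48% to 100%) |
| Surgery as scheduled, group of 3 | 2/3 = 67% (9% to 99%) | 2/2 = 100% (16% to 100%) |
| DLTs, expanded Cohort E group, if tabulated on the FAS | 1/6 = 17% (0.4% to 64%) | 0/5 = 0% (0% to 52%) |
| DLTs, Cohort F, if tabulated on the FAS | 1/3 = 33% (0.8% to 91%) | 0/2 = 0% (0% to 84%) |

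The DLT row for Cohort E uses six patients because Section 3 expands a group of three to six after one DLT, so 1/3 is not a final result there. Cohort F has three patients and no expansion rule is stated, so a final 1/3 can occur only in that cohort.

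**4. How often it could arise**

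The documents give no rate of ineligibility found after dosing. For an assumed rate q per patient, the chance of at least one such patient among n is 1 − (1 − q)^n.

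| Assumed q | n = 6 | n = 12 | n = 15 |
|---|---|---|---|
| 2% | 11% | 21% | 26% |
| 5% | 26% | 46% | 54% |
| 10% | 47% | 72% | 79% |

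For example, 1 − 0.95^15 = 0.537. These are chances that an exclusion is possible at all, not that the excluded patient has the event.

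**The case against.** The best defence has three parts.

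- **Meaning of eligible.** Section 6.1 has eligibility settled before treatment, and footnote a of Table 1 has registration follow confirmation of all criteria. Eligible could then mean confirmed eligible before dosing, which would keep a patient whose breach emerges later. The text allows this reading but does not state it. If it is the intended one, every properly registered and dosed patient qualifies, the word does no work and can be removed without loss. A patient dosed in error without confirmation would still be left out of safety.
- **Documents not seen.** Section 7.2 has a carve-out for other specifications, and the master protocol or the SAP may define an all-treated set. This stands as a limit on certainty. It does not change what the substudy protocol states as its default.
- **Other safeguards.** Adverse events are collected to 30 days after dosing with no eligibility condition, and the DSMC reviews any SUSAR. That protects patients during the study, but it does not determine the denominators in the reported tables.

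A reader might infer more than the documents support. One might conclude that 3+3 decisions or accrual suspension would be taken on the restricted set; Sections 3 and 6.4 give those rules a different basis. One might treat it as settled that the DLT tables drop such patients, so that the reported DLT rate no longer matches the dose decision; the separate DLT-evaluable term points to another denominator, which is defined elsewhere if at all. And one might count T2 disease first found at the study resection as a breach; exclusion criterion 6 concerns a history of T2 disease, so only undisclosed prior T2 is a clear example.

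**Conclusion.** The concern holds for the reported adverse event summaries and the primary surgery endpoint. As written, a dosed patient judged not to meet a criterion is outside the only set used for safety, and nothing prevents that judgement from being made after the outcome is known.

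One such exclusion can move surgery as scheduled from 83% to 100% in a group of six. It can move DLTs from 17% to 0% in an expanded Cohort E group only if DLT tables are built on the FAS, which remains open.

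The sizes assume that the excluded patient is the one with the event. The conclusion assumes the literal reading of eligible and no contrary definition in the master protocol or SAP. How likely it is in practice cannot be estimated from the documents. It is still a stated rule acting on the primary safety endpoint, not just a missing detail, and should be corrected before the SAP is finalised.

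**What to change.** In Section 7.2, the synopsis and the SAP, do one of the following:

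- delete the word eligible from the FAS definition; or
- preferably, define a Safety Set of all patients who received any amount of PVSRIPO or, in Cohort F, any study wash, regardless of eligibility and analysed as treated.

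The second option also covers a Cohort F patient who has the washes but not the virus. Table 4 lists only PVSRIPO as a study drug, so deleting one word would not clearly bring that patient in.

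Use this set for adverse events, shedding and the surgery endpoint. Report DLT frequency on it alongside the DLT-evaluable set, and define or cross-reference that term. If an eligible-only set is wanted, keep it as a sensitivity set for the infection endpoint. If the master protocol already holds an all-treated set, cite it in Section 7.2.

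The cost is a few sentences in three places. No extra patients, visits or data are needed.

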7.3. Timing of Planned Analyses

Planned safety analyses by the DSMC are outlined in [Section 6.4](#).

7.4. Statistical Analysis Methods

A SAP will be developed and finalized prior to the first planned database lock and will include more details related to the statistical analysis of this study's data. This section is a summary of the key aspects of the planned statistical analyses.

7.4.1. General Considerations

All statistical analyses will be performed using appropriate statistical software. The exact software and versions will be described in the SAP.

Data will be summarized descriptively by treatment group. The descriptive summary for the categorical variables will include counts and percentages. The descriptive summary for the continuous variables will include means, medians, standard deviations, 25% and 75% percentiles, and minimum and maximum values.

7.4.2. Demographic and Baseline Characteristics

Demographics and baseline characteristics will be summarized for the FAS population descriptively by treatment and overall.

7.4.3. Prior and Subsequent Anticancer Therapies

Prior and subsequent anticancer therapy verbatim terms will be coded to Anatomical Therapeutic Class (ATC) and preferred term using the most recent WHO-DD. For the FAS population, summary statistics will be provided for prior or subsequent systemic anticancer therapies by treatment group and overall. For the subsequent systemic anticancer therapies, the lines of therapy, response to each treatment regimen, and disease progression status will also be summarized by treatment group and overall.

7.4.4. Efficacy Analyses

The proportion of patients with demonstrable PVSRIPO infection of excised tumor tissue by dose group and cohort will be described.

7.4.5. Safety Analyses

Refer to [Section 7.4.5 of the Master Protocol](#).

Additional safety analyses specific for NMIBC will include the number and percentage of patients who undergo TURBT or cystectomy.

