PVSRIPO Shedding: Stool ^h			X	X	X

Protocol Activity	Screening Period	DLT Period			Day 30 (± 2 Days) ⁱ
		Cycle 1		End of Treatment	
	≤ 28 Days	Day 1	Day 2-5	Day 14 (+3 Days)	
Blood Samples for Biomarker and Cytokine Analysis	X (serum prior to Polio Vaccine booster)	X (predose)	X	X	X
Other Clinical Assessments					
Adverse Events ^j		AEs up to 30 days post dose			
Concomitant Medication and Non-Drug Supportive Interventions		Con meds up to 30 days post dose			

AE=adverse event; Con meds=concomitant medications; DLT=dose-limiting toxicity; ECG=electrocardiogram; ECOG=Eastern Cooperative Oncology Group; TURBT=transurethral resection of bladder tumor; WOCB=women of childbearing potential.

^a Patient registration should be completed after all eligibility criteria are confirmed and as close to Cycle 1 Day 1 as possible.

^b Vital signs: includes temperature (oral, tympanic, or axillary), blood pressure, and pulse rate to be recorded in the sitting position after 5 minutes of rest.

^c Cardiologist review is not required for Screening ECG.

^d If the screening assessments are conducted within 3 calendar days prior to Cycle 1 Day 1, they do not need to be repeated.

^e Images to be obtained prior to instillation on the day of PVSRIPO intravesical instillation, and prior to surgical resection on the day of TURBT or cystectomy.

^f See [Section 6.3](#) for details regarding tissue biopsies.

^g All urine samples should be collected as described in the lab manual. On Cycle 1 Day 1, the pre-dose urine sample should be collected within 1 calendar day prior to PVSRIPO instillation. On Cycle 1 Day 1, the patient should void in the toilet after the 2-hour instillation and the next first voided urine sample should be collected for PVSRIPO Shedding. Urine samples should also be collected on Days 2, 4, 6, 8 and 14 of Cycle 1. If the day of the TURBT/cystectomy happens to coincide with a urine collection day, the urine sample should be collected prior to the surgery.

^h All stool samples should be collected as described in the lab manual.

ⁱ Refer to [Master Protocol Section 6.1](#) for details on adverse event reporting.

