With respect to the risk of delayed curative resection due to localized inflammation, the published literature reviewed in [Section 1.1.2](#) suggest that inflammation induced by intravesicular or cystoscopic administration of oncolytic viruses does not preclude curative resection. Therefore, it is expected that administration of PVSRIPO via intravesical instillation, will also not preclude curative resection. Patients in this substudy will only receive 1 instillation of PVSRIPO followed by TURBT or curative resection after 2-5 days; therefore, the delay will be minimal.

As a result of administration of PVSRIPO via cystoscopy, there is the potential for viral shedding of PVSRIPO directly into the urine of treated patients. Therefore, urine viral shedding studies

will be conducted as outlined in this substudy and in Schedule of Assessments ([Table 1](#)). However, even if PVSRIPO is detected in the urine, the potential for clinically significant toxicity to the patient or associated household contacts is predicted to be nominal given the following observations:

- Limitation of systemic spread by the immunologic recall responses initiated by the booster vaccine required prior to enrollment of the patient.
- Elimination of neurovirulence by the foreign internal ribosome entry site (IRES).
- Near universal poliovirus vaccination status of the global population.
- Compromised replication in non-malignant CD155⁺ cells.
- Limited cell types that express CD155.

Additional details on the risk of viral shedding to household contacts are provided in the master protocol ([Master Protocol Section 1.1.4.1](#)).

For those patients enrolled in **Cohort F**, there is a potential risk for increased bladder irritation associated with pretreatment of the bladder with 5% DDM. This risk is predicted to be low to negligible based on published literature indicating that intravesical instillation of 0.1% DDM in mice and rats did not result in clinically relevant irritation and that this procedure is being used in patients receiving CG0070 ([Burke 2012](#), [Ramesh, 2004](#)).

Taken together, the data generated to date suggest PVSRIPO is well-tolerated and that PVSRIPO may have direct anti-tumor activity. Therefore, the overall risk/benefit ratio is favorable.

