2.1.1. Safety

Since surgical resection (TURBT or cystectomy) is one component of the standard of care treatment for patients with recurrent NMIBC, it is important to evaluate whether PVSRIPO administered via intravesical instillation impacts the ability of a patient to undergo surgical intervention.

As described in the master protocol and in the Investigator's Brochure (IB), PVSRIPO has been subjected to extensive nonclinical and clinical viral shedding studies, all of which suggest the risk of extra-tumoral PVSRIPO dissemination and shedding is extremely low. However, because PVSRIPO shedding in patients with NMIBC receiving PVSRIPO via intravesical instillation has not been characterized, it is important to evaluate the potential for shedding of PVSRIPO in the urine for these patients. In addition, since PVSRIPO is a replication-competent enterovirus, it is important to determine if the virus is shed in the stool after intravesical instillation, an analysis which could indicate systemic spread of the virus beyond the site of administration within the bladder.

The timepoints of stool and urine sample collection for viral shedding analysis ([Table 1](#)) were chosen based on the following considerations:

5. Ease of sample collection and patient burden.
6. Timing of stool sample collection in patients with glioblastoma multiforme (GBM) evaluated for viral shedding (Week 1, 2, 4, and 8 after one intracerebral infusion of PVSRIPO) ([Section 6.2.7; Final Clinical Shedding Study Report for PVSRIPO for Recurrent Glioblastoma \[GBM\] dated August 6, 2017 \[IND 14735, Serial 0131\]](#)).
7. Food and Drug Administration (FDA) guidance titled "Design and Analysis of Shedding Studies for Virus or Bacteria-Based Gene Therapy and Oncolytic Products," which suggests "shedding is most likely to occur in the period immediately following product administration", and that a "second peak of shedding may be noted in the days/weeks after administration of a replication competent product as a result of its multiplication/amplification in vivo".
8. Timing of urine sample collection in animal studies (Day 14, 28, and 56 after intrathalamic inoculation of *Macaca fascicularis* with PVSRIPO on Day 0) ([Dobrikova 2012](#)).
9. After intratumoral injection or intravesical instillation, PVSRIPO is predicted to replicate within the tumor for approximately 1-2 weeks.
10. Alignment of shedding time points across bodily fluids (including urine) being evaluated in the PVSRIPO program.

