The dose of PVSRIPO administered in **Cohort F** will be the highest dose evaluated in **Cohort E** which does not exceed the maximum tolerated dose. Since the bladder washes implemented in **Cohort F** are predicted to improve PVSRIPO infectivity of the bladder mucosa, the highest tolerable PVSRIPO dose administered without washes was chosen to maximize potential patient benefit. As discussed above, preclinical and clinical data suggest that adding washes to the intravesical instillation of viruses does not increase clinically relevant toxicity (Burke 2012).

The timing of PVSRIPO administration prior to TURBT or cystectomy was chosen to be 2 to 5 days based on the following criteria:

1. Delaying TURBT or cystectomy by 2-5 days is not predicted to have a substantial impact on the clinical outcomes of the patients.
2. Preclinical studies with intratumoral injection of PVSRIPO suggest that PVSRIPO replication lasts for approximately 1-2 weeks after injection with peak viral load within 5 days of injection, such that PVSRIPO should still be detectable in the tumor tissue (Yang 2021).
3. Preclinical studies suggest that the innate immune effects of intratumoral injection of PVSRIPO peak before 5 days post treatment such that collecting tissue at 2-5 days will optimize the probability of seeing an effect.

PVSRIPO in combination with anti-PD-1/L1 therapy is not being investigated in this substudy because NMIBC has an exceedingly good prognosis such that systemic therapies with their associated toxicities are generally not used in this patient population because of the poor risk/benefit profile.

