The dose and dose escalation approach for PVSRIPO is described in [Section 3](#). The timing of administration is outlined in [Table 1](#); in general, PVSRIPO will be administered 2-5 days prior to TURBT or cystectomy.

PVSRIPO preparation, handling, and administration should be performed in accordance with the Pharmacy Manual.

Only staff trained in cystoscopy and intravesical instillation who have read the Pharmacy Manual are allowed to administer PVSRIPO.

Patients should not have a UTI at the time of treatment, as determined by the Investigator. Prophylactic antibiotics should be administered 1-3 days pre-treatment, on the treatment day, and 1-3 days post-treatment to reduce the likelihood of a procedure-related UTI.

Anticoagulant and antiplatelet medications will be managed by the treating physician, per local institutional guidelines, to optimize the safety of intravesical instillation of PVSRIPO.

Investigators should confirm that patients are suitable for the administration procedure prior to each planned administration of PVSRIPO.

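### The primary endpoint requires surgery as scheduled, but Section 7.4.5 counts any TURBT or cystectomy, so as written a toxicity-delayed operation scores as a success

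*Combined protocol and SAP*

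**What the plan says.** **Endpoint.** The synopsis and Table 3 (Section 2) give the same substudy-specific primary endpoint for both cohorts: "Proportion of patients who undergo TURBT or cystectomy as scheduled". Section 2.1.1 explains its purpose: "it is important to evaluate whether PVSRIPO administered via intravesical instillation impacts the ability of a patient to undergo surgical intervention". Section 1.2 lists a delay to curative resection among the potential risks. It then argues that the delay should be small, since each patient has a single instillation "followed by TURBT or curative resection after 2-5 days; therefore, the delay will be minimal".

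**Analysis.** Section 7.4.5 refers to the master protocol for the general safety analyses and adds one sentence for this population: "Additional safety analyses specific for NMIBC will include the number and percentage of patients who undergo TURBT or cystectomy". It gives no schedule, date or time limit. No other analysis of the endpoint is stated, and the protocol does not say what counts as on schedule. The default population is the FAS, meaning eligible patients who received at least one dose (Section 7.2). Categorical data are summarised by counts and percentages (Section 7.4.1).

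**Timing of surgery.** Table 1 puts the instillation in the Day 1 column and surgery in the Day 2-5 column. A footnote to Table 1 ties Day 1 to dosing: "On Cycle 1 Day 1, the pre-dose urine sample should be collected within 1 calendar day prior to PVSRIPO instillation". Section 3.1 says: "The timing of PVSRIPO administration prior to TURBT or cystectomy was chosen to be 2 to 5 days". Section 5.1.1.1 points to Table 1 for timing and then states: "in general, PVSRIPO will be administered 2-5 days prior to TURBT or cystectomy".

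**The concern.** The endpoint and its analysis differ in the one condition that carries the safety question. Everyone enrolled is already intended for TURBT or cystectomy. The harm to look for is therefore mainly that surgery is put off because of inflammation or an adverse event. A patient whose operation is postponed for that reason fails the endpoint in Table 3 and passes the count in Section 7.4.5.

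A count of patients ever operated on is also likely to sit near its ceiling. The protocol's own precedents suggest this: in the three studies in Section 1.1.2 that had planned surgery after instillation or injection, 11 of 12, 4 of 4 and 15 of 15 patients were operated on, or 30 of 31. The one exception was unresectable disease. These studies are small and two of them were in muscle-invasive disease, so the figure is only indicative. A reported 100% could then be read as evidence that the drug does not interfere with surgery when the count was not able to show a delay.

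**Working it through.** **1. Group sizes.** Section 3 plans two dose levels in Cohort E, and Section 7.1 plans 3 to 6 patients at each. That gives 2 × 3 = 6 and 2 × 6 = 12, which reproduces the stated range of 6 to 12. Cohort F has 3 patients (synopsis). The plan states no null rate, margin, alpha or power for this endpoint, so there is no power calculation to repeat.

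**2. The same data under the two rules.** Suppose all n patients in a group are operated on and k of them late. The Table 3 rule gives (n − k)/n. The Section 7.4.5 rule gives n/n. The difference is k/n. For k = 1:

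| n | Table 3: as scheduled | Section 7.4.5: any surgery | Difference |
|---|---|---|---|
| 3 | 2/3 = 66.7% | 3/3 = 100% | 33.3 points |
| 6 | 5/6 = 83.3% | 6/6 = 100% | 16.7 points |
| 12 | 11/12 = 91.7% | 12/12 = 100% | 8.3 points |

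The rows for 3 and 6 are the dose groups. The row for 12 is Cohort E at its largest, with dose levels pooled.

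**3. How likely the rules are to disagree.** The documents give no rate of delayed surgery, so the rate q is an assumption, taken here as 10% to 30%. If every patient is eventually operated on, the chance that at least one operation in a group is late is 1 − (1 − q)^n.

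| q (assumed) | n = 3 | n = 6 |
|---|---|---|
| 10% | 27% | 47% |
| 20% | 49% | 74% |
| 30% | 66% | 88% |

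Over this range, disagreement in a given dose group is an ordinary event.

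**4. The two statements of the surgery window.** With dosing on Day 1, study day = 1 + days after dosing.

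- Table 1: study Days 2, 3, 4, 5, which are 1, 2, 3, 4 days after dosing.
- Sections 1.2, 3.1 and 5.1.1.1: 2, 3, 4, 5 days after dosing, which are study Days 3, 4, 5, 6.

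The two agree on Days 3, 4 and 5. Day 2 is allowed only by Table 1, and Day 6 only by the text.

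**The case against.** The strongest reply is that Section 7.4.5 is shorthand. The endpoint carries its schedule condition each time it is stated. Section 7.4 describes itself as a summary and leaves detail to a separate SAP, and Section 7.4.5 also relies on a master protocol section that is not part of the documents reviewed. Section 7.4.1 provides counts and percentages that could be applied to the endpoint as Table 3 defines it. This stands as a limit on wording: the claim is about what Section 7.4.5 does if followed as written, and the sponsor's intention cannot be known. It does not remove the point. The written rule is still the only one given. The SAP is due only before the first planned database lock, in a study that describes sequential dosing with no control group and no blinding. A definition settled then could be settled with the delays already known.

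A second reply is that little depends on this number. Escalation follows dose-limiting toxicities over 14 days with DSMC consultation, and no threshold or decision uses the surgery proportion. Adverse events are collected to 30 days after dosing, so an event that caused a delay should be on record, and groups of 3 to 6 can be reviewed patient by patient. All of this stands. The consequence is confined to the reported primary endpoint.

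A reader might also infer that the two surgery windows are incompatible and that this is what turns a delay into a success. The documents do not support that. The windows are one day apart and share three of four days, and Section 5.1.1.1 qualifies its range as general. The delay problem comes only from the condition missing in Section 7.4.5. The offset would affect the endpoint only if on schedule means within the protocol window, which the protocol does not say; it could equally mean the patient's own planned date.

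**Conclusion.** The point holds in this form: the primary endpoint for both cohorts is surgery as scheduled, and the only analysis stated for it counts surgery at any time. Applied literally, each operation delayed by toxicity is scored as a success and raises the reported proportion by 33 points in a group of 3 or 17 points in a group of 6. This rests on the wording of Section 7.4.5 and on no fuller definition being given elsewhere; a SAP or master protocol text that restores the condition would settle it. The 10% to 30% delay rates above are illustrative, and the conclusion does not depend on them.

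Two stronger readings are not supported. Dose escalation is not compromised, since it does not use this endpoint. Nor does the plan hide the denominators, since Section 7.4.5 promises a number as well as a percentage. The absence of exact confidence intervals is not an error in a descriptive 3+3 study.

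The one-day difference between Table 1 and the text is a separate and smaller inconsistency. The passages need to be reconciled; this review takes no view on which window is right.

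**What to change.** 1. In Section 7.4.5 and the SAP, replace the sentence with the number and percentage of FAS patients whose TURBT or cystectomy took place as scheduled, by dose group and cohort.
2. Give one definition of as scheduled, fixed before dosing. One example is surgery on or before the date recorded for that patient before the instillation. Do not combine this with a protocol-window rule: an operation planned for Day 3 and moved by an adverse event to Day 5 lies inside both stated windows and is still late.
3. List every delayed or unoperated patient with days of delay and reason (adverse event, logistics, other).
4. Show the count of patients ever operated on only as a supporting line.
5. Separately, reconcile Table 1 with Sections 1.2, 3.1 and 5.1.1.1 so that surgery timing is stated with one day count from dosing.

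Exact confidence intervals are optional; for orientation, the 95% Clopper-Pearson interval is 29% to 100% for 3/3 and 9% to 99% for 2/3.

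The cost is a small wording change, a planned surgery date recorded before dosing if that definition is chosen, and a percentage that may look less favourable. Sample size and the escalation scheme do not change.
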